**Addressing Social Determinants of Health & Diabetes Self-Management
in Vulnerable Populations**

STATISTICAL ANALYSIS PLAN

NCT# 03802825

Date: April 21, 2021 (Published version)

Statistical and Qualitative Analysis Plan

Before we carry out any analyses, we will audit the data for quality and completeness, and evaluate missing data patterns. We will examine variable distributions for outliers and assess them to ensure that they meet the assumptions of the planned analysis. We will present the baseline characteristics as means and standard deviations for continuous variables and as percentages for categorical variables. Nominal variables will be coded as categorical variables for inclusion as predictors in multivariate analyses. All inferential tests will be carried out at a two-tailed alpha level of .05. We will examine group differences on important baseline factors using a student t- test (or the nonparametric Mann-Whitney U test) for continuous variables and chi-square test (or the Fisher's exact test) for categorical variables. Significant variables will be included as covariates in the models.

Recruitment and retention rate, proportion of participants with a successful referral to a patient navigator and CHW, mean number of days to connect each participant to a navigator and CHW, and proportion of participants with unmet basic needs met at 6-month follow-up will be calculated as described in Table 1. For the qualitative analysis, a coding dictionary will be developed based on review of the transcripts' content and interview questions. Codes will denote content of questions, TICD and PRISM domains, and concepts naturally emerging from the discussions. During the coding process, inter-rater reliability will be established by comparing the agreement in coded text with 20% of the transcripts between two coders. Any differences in coding will be resolved through discussion, and the two coders will meet regularly to discuss and refine the coding process. A qualitative database will be compiled, coded, and analyzed using a qualitative software program (Dedoose). Once all transcripts are coded within the software program, we will use text retrieval and grouping functions on specific codes and combinations of

codes for a particular topic and summarize the issues, agreements, and disagreements in the content for each item. This process will result in a list of themes relating to intervention acceptability[42] and determinants (barriers and facilitators) of implementation and sustainability. As we summarize and interpret, we will identify findings or patterns among themes and will review data for statements that directly confirm or discredit our interpretations.[43-45]

To assess preliminary effectiveness, using a chi-square test, we will compare the two study arms on proportion of participants with A1C < 8% at 6-month follow-up. In addition, we will conduct a logistic regression analysis to assess the association between the study arms and A1C < 8% at 6-month follow-up, coding the study arms as a binary variable (Navigation only as the reference) as the predictor of interest. We will control for factors that are not balanced between the two arms (e.g., age, sex) in the model. We will conduct similar analyses for the binary outcome, A1C test completed (yes or no).

To analyze the number of emergency department (ED) visits by each participant, we will count and then summarize the distribution of the ED count with means, medians, standard deviations, quartiles, frequency, and proportion of participants with 0, 1, 2+ ED visits, by study arm. We will use the Poisson model (or negative binomial model when appropriate) to analyze the relationship between study arms and the number of ED visits adjusting for the covariates that are significantly different between the two arms. We will report the estimated rate ratio (RR) associated with the study arm binary variable and the 95% CI.

The primary care no-show visit rate will be calculated as the number of primary care visits a participant missed divided by the total number of primary care visits scheduled during the 6-month follow-up period. The time to refill a medication will be based on number of days

between the diabetes medication being dispensed and the previous supply running out. Delayed refills will be defined as medication not being dispensed for 7 days or more after the previous supply ran out. For each participant, number of delays or gaps in refills and number of days without a refill will be calculated. Both no-show visit rate and number of delays in refills are continuous variables. We will summarize the distributions with means, medians, standard deviations, and quartiles for each study arm. Assuming normal distribution, we will use the two-sample t-tests to compare the means of these two outcomes between the two study arms. We will use multiple linear regression modeling to examine the association between study arms and these two outcomes. Based on expectations of fairly well-balanced study arms for these two outcomes we will adjust for all unbalanced factors in the models. We will report the coefficients and the 95% CIs associated with the study arm binary variable.

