Qualitative interviews will be conducted with various stakeholders to assess intervention acceptability and several implementation domains including intervention burden, professional interactions (referral processes and communication across different levels of care), and capacity for organizational change. Preliminary

effects on A1C, diabetes-related care gaps, health care utilization, and medication adherence will also be examined.

The two treatment arms are summarized in the figure below.

5. Study Population

For Phase 1, using the electronic health record system at Kaiser Permanente Northwest (KPNW), we will identify patients that meet eligibility criteria.

Inclusion criteria:

- Diagnosis of diabetes
- Current Kaiser Permanente Northwest member
- African American, Hispanic/Latino (English, Bilingual, or Spanish speaking only), and/or a Medicaid recipient (from any racial or ethnic background)
- Age 18 or older
- Most recent hemoglobin A1C $\geq 8\%$

Phase 2 Inclusion criteria:

- Diabetes diagnosis
- Current Kaiser Permanente Northwest member
- African American, Hispanic/Latino (English, Spanish-speaking, or bilingual), and/or a Medicaid recipient (from any racial or ethnic background)
- Age 18 or older
- Most recent hemoglobin A1C test of ≥ 8
- Endorses 1 or more social and/or economic need on the YCLS

Because patient-level socioeconomic status (SES) is not captured in the EHR, we will identify eligible patients based on SES using their health insurance coverage type, Medicaid.

Exclusionary criteria:

- Patients who are unable to provide verbal informed consent due to cognitive or psychiatric impairment
- Patients with a HIV+ diagnosis

Phase 3 Inclusion criteria:

- Current Kaiser Permanente Northwest member
- Age 18 or older
- Identifies as Asian American, Pacific Islander, Native Hawaiian, and Alaska Native
- Most recent hemoglobin A1C \geq 8%

a. Vulnerable Populations

African Americans, Hispanics, and Medicaid recipients with poorly managed diabetes who will be recruited for this study certainly meet the general definition of 'vulnerable population' given that they represent the disadvantaged sub-segment of the community requiring high quality care and special considerations and protections in research. We will follow a strict protocol in terms of confidentiality. We will not intentionally target or include data from members of other vulnerable populations such as children, pregnant women, prisoners, or employees.

b. Setting

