KPNW is a non-profit, group model integrated health care system that provides comprehensive prepaid health care to its more than 550,000 members in southwest Washington and northwest Oregon. It owns and operates two hospitals, contracts with six other local hospitals, and maintains 22 medical clinics (17 with primary care). All patient contacts within the system and all services referred outside are recorded in a single, comprehensive electronic health record (EHR, KP HealthConnect, based on Epic[®]) that has been in place since 1996. Health and health care utilization data is stored in the Virtual Data Warehouse (VDW), which is maintained by the Kaiser Permanente Center for Health Research. The VDW provides a standardized, distributed data warehouse for the EHR and other clinical and administrative informatics systems employed by the health system. The VDW includes files for all encounters (outpatient and inpatient), vital signs, pharmacy fill data, problem lists and encounter diagnoses, procedures, and laboratory results.

c. Informed Consent Waiver and HIPAA Privacy Rule Waiver of Authorization

Because Phase 1 is a data-only study, we request a waiver of written and signed consent as well as HIPAA authorization for the study to extract participant data from the EHR (e.g., demographics, primary language spoken, contact information, clinic paneled to, vital signs, labs, diagnoses, encounters). At enrollment KPNW members are informed that their medical records may be used for research and that they may choose to opt out of such research; CHR maintains a registry of members who have asked not to be included in research or to have their records used, or both.

For Phase 2, we also request a waiver of written and signed consent as well as HIPAA authorization. Verbal informed consent by the participant will be captured and recorded in REDCap by study staff during the initial recruitment call and after study eligibility has been determined. No study activities or data collection will be gathered until after verbal informed consent has been obtained.

For Phase 3, we are also requesting a waiver of written consent as well as HIPAA authorization for the study to extract participant data from the EHR (e.g., demographics, clinic, primary language spoken, medical diagnosis, most recent A1C, most recent blood pressure measurement, BMI, insurance coverage, existing YCLS data, and social diagnosis codes).

6. Procedures

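### Covariates are chosen by baseline significance tests, so baseline A1C and prior ED, no-show and refill values would each enter their model at most about 5% of the time

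*SAP*

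**What the plan says.** The opening paragraph of the SAP's Statistical and Qualitative Analysis Plan sets the level: "All inferential tests will be carried out at a two-tailed alpha level of .05". It continues: "We will examine group differences on important baseline factors using a student t- test (or the nonparametric Mann-Whitney U test) for continuous variables", with chi-square or Fisher's exact tests for categorical variables. The consequence is: "Significant variables will be included as covariates in the models". The factors to be tested are not listed.

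The outcome paragraphs then restate the rule:

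- A1C <8%, and by extension A1C test completed: "We will control for factors that are not balanced between the two arms (e.g., age, sex) in the model".
- ED visits: the Poisson or negative binomial model is fitted "adjusting for the covariates that are significantly different between the two arms".
- No-show rate and refill delays: "Based on expectations of fairly well-balanced study arms for these two outcomes we will adjust for all unbalanced factors in the models".

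No criterion for imbalance other than significance appears anywhere. Age and sex are the only examples given. Neither document names baseline A1C, prior ED visits, prior no-show rate or prior refill delays as a covariate, and the protocol describes no stratification of the randomization.

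**The concern.** Participants are individually randomized (Protocol Section 6), so every baseline difference between arms is due to chance. A baseline p-value measures how large that chance difference happened to be. It does not measure whether the variable predicts the outcome, which is what decides whether adjustment helps. A strong predictor just short of significance is left out, while an irrelevant factor that happens to pass is put in.

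Three things are at stake. The adjusted models lose the precision that a prognostic baseline value would give. Moderate chance imbalance in such a value stays in the estimate. The adjustment set is also unknown until the trial's own data have been examined. For the no-show and refill models the SAP itself expects well-balanced arms, so its rule would normally adjust for little or nothing.

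**Working it through.** The documents give no power calculation, so there is no stated figure to reproduce.

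**Inputs from the documents.** Alpha .05 two-sided (SAP, opening paragraph); 50 per arm (Protocol Section 6); baseline A1C of at least 8 (Protocol Section 5, Phase 2 inclusion); a mean A1C benefit of 0.31 points for self-management interventions (Protocol Section 3). Correlations, ED rates and all other effect sizes below are assumptions.

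**Step 1: chance of entry.** Under randomization the null hypothesis is true for every baseline variable, so P(entry) = P(p < .05) = 0.05. Simulating 20,000 trials with 50 per arm and plausible distributions gave these t-test / Mann-Whitney rates: A1C 4.9% / 5.1%; ED count 4.7% / 4.8%; no-show proportion 5.1% / 5.0%; refill delays 4.8% / 5.1%. If ten independent factors were tested, at least one would enter by chance in 1 − 0.95^10 = 40% of trials.

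**Step 2: imbalance left uncorrected.** The standard error of a standardized baseline difference is √(2/50) = 0.20. The significance threshold is t(.975, 98) × 0.20 = 0.397 SD. The median absolute imbalance is 0.6745 × 0.20 = 0.135 SD.

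**Step 3: linear models (no-show, refill).** With baseline-outcome correlation r, the variance under the rule relative to always adjusting is roughly 1 + k·r²/(1 − r²). Here k = 0.95 − 2 × 1.96 × φ(1.96) = 0.95 − 0.229 = 0.721, because the 5% of trials with the largest imbalance do get adjusted. This gives 1.03, 1.07, 1.24 and 1.69 at r = 0.2, 0.3, 0.5 and 0.7. Estimating the slope costs the adjusted model about 1%, which lowers these slightly. Simulation with 8,000 trials per correlation and an assumed 0.5 SD effect gave:

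| r | Power, SAP rule | Power, always adjusted | Variance ratio |
|---|---|---|---|
| 0.2 | 69.7% | 71.0% | 1.03 |
| 0.3 | 70.8% | 74.3% | 1.06 |
| 0.5 | 69.9% | 80.2% | 1.22 |
| 0.7 | 70.3% | 92.8% | 1.66 |

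Monte Carlo error is about √(0.7 × 0.3/8000) = 0.5 points at 70% power. A repeat with 40,000 trials gave 70/71/72% against 73/81/93% at r = 0.3/0.5/0.7. With no true effect, the rule rejected in 4.8%, 4.2% and 3.7% of trials, against about 5% when always adjusted, so the rule is mildly conservative.

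**Step 4: A1C <8% logistic model.** Assumed model: baseline = 8 + gamma(1.4, 1.25); 6-month value = 9.2 + 0.5 × (baseline − 9.75) − effect + N(0, 1.35). Reference-arm P(<8%) is 21.6%; there were 4,000 trials per effect.

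| Shift | P(<8%), training arm | Power, rule / always | Median SE | Median OR |
|---|---|---|---|---|
| 0.31 | 28.7% | 12.0% / 13.1% | 0.470 / 0.497 | 1.47 / 1.52 |
| 0.8 (assumed) | 40.5% | 52.3% / 57.2% | 0.454 / 0.483 | 2.49 / 2.79 |

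The SE does not shrink. The gain comes from a conditional odds ratio that lies further from 1.

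**Step 5: ED model.** Assumed person-level rates: gamma with shape 0.8 and mean 0.5 or 1.0 visits per 6 months. Prior and follow-up counts share the same person rate (correlation 0.37 to 0.54). The fit is negative binomial with log(1 + prior visits), over 1,200 trials per scenario. The variance ratio for the log rate ratio, rule against always adjusting, was 1.07 and 1.20 at a true rate ratio of 0.5, and 1.03 and 1.23 at 1. Null rejection was 3.7% to 5.3% under the rule and 6.2% when adjusted, so ED power is not compared.

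**The case against.** This is a feasibility pilot with preliminary effectiveness aims and no power claim. The chi-square and two-sample t-tests use no covariates and are untouched by the rule; only the accompanying regressions are affected, and ED visits are the one outcome with no separate unadjusted test. The A1C gain is about one point of power at the only effect size the documents supply. The large contrasts need correlations of 0.5 or more, which a no-show rate based on few visits may not reach. Normal data are also a rough stand-in for a bounded rate and a count. The ED simulation assumes stable person-level rates, which favors adjustment. All of this stands and limits the size of the point.

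The 5% can also be questioned. If a variable is not among the unlisted factors tested, its chance of entry is zero, so 5% is a ceiling under the stated rule. *Unbalanced* might instead mean a size threshold: at 0.2 SD, entry would be P(|Z| > 1) = 32%. No such threshold is stated, though, and a looser reading leaves the covariates to post hoc judgment.

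The 6.2% null rejection of the adjusted ED model is (6.2 − 5)/√(5 × 95/1200) = 1.9 standard errors above nominal. It is borderline, but worth checking before that model is fixed.

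Finally, the SAP is dated April 2021, while the protocol anticipated a September 2018 start and a two-year timeline. If outcomes by arm had already been seen, a change now is not prespecification.

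None of these objections defends selecting covariates by baseline p-value. The SAP plans adjusted models with confidence intervals, and those should be fixed in advance.

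**Conclusion.** The concern holds. The SAP's only operational covariate rule gives each tested baseline variable about a 5% chance of entry and an untested one none, and nothing in either document fixes a prognostic covariate. This follows from the SAP's alpha and from randomization, and needs no further assumption.

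The size of the loss does rest on assumptions. It is small for A1C <8%, and 1 to 4 power points for the linear models at correlations of 0.2 to 0.3. It is about 10 points at 0.5 and more above that. For ED visits it is a 7% to 20% variance penalty at the assumed rates and a rate ratio of 0.5. There is no systematic bias and no inflated type I error in the linear models. The change should be made because it is cheap and settles the adjusted models in advance; the pilot's feasibility aims do not depend on it.

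**What to change.** Delete the significance-based covariate rule and the baseline p-values; keep the descriptive baseline table. Name these covariates, to be included regardless of observed balance:

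- **A1C <8%:** most recent pre-randomization A1C, continuous. Every participant has one, since Protocol Section 5 requires "Most recent hemoglobin A1C test of" at least 8.
- **ED visits:** log(1 + ED visits in the prior 6 months).
- **No-show rate:** prior-year no-show rate.
- **Refill delays:** delays in the prior 6 months, using the same 7-day definition.
- **A1C test completed:** a prior A1C result is an entry criterion, so there is no varying baseline value. Report it unadjusted, or with a small covariate set fixed in advance.

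Where a baseline value is undefined (no scheduled visits, no diabetes fills, or too short a membership for the ED look-back), set it to a constant and add a missing indicator. The functional forms and look-back windows are reasonable choices; what matters is fixing them beforehand. Label the adjusted odds ratio as conditional, and keep the planned chi-square and t-tests as the unadjusted results. If outcomes by arm have already been examined, say so and report the revised models as post hoc.

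The cost is SAP wording, one or two degrees of freedom per model, and a short look-back extraction. Protocol Section 5b states that "The VDW includes files for all encounters (outpatient and inpatient), vital signs, pharmacy fill data" are already held.

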Aim 3: Assess preliminary effectiveness by comparing the two study arms on the following outcomes at 6-months post-randomization: a) proportion of patients with A1C $<$ 8%; b) proportion of patients with an A1C test; c) number of emergency department visits; d) primary care visit no-show rate; and e) percent of on-time pharmacy refills for diabetes-related medications.

Phase 3

Aim 1: Extract clinical data on Asian American, Pacific Islander, Native Hawaiian, and Alaska Native populations in KPNW from the EHR as preliminary data for a future grant proposal including these populations in a large-scale, pragmatic, randomized trial aimed to address disparities in diabetes management in relation to socioeconomic needs.

3. Background

Racial/ethnic minorities and low-income individuals in the U.S. are less likely to achieve diabetes-related clinical targets. Only 42% of African Americans and 38% of Hispanics with diabetes have hemoglobin A1C

levels at target ($\leq 7\%$), compared to 58% of Whites.¹ In addition, individuals with low socioeconomic status (of all racial/ethnic backgrounds) are also more likely to have suboptimal diabetes management.^{1,2} This is troubling because poor diabetes management leads to an increased risk for diabetes complications including cardiovascular disease events, contributing to the disparities in the rates of these major diseases.³ As such, pragmatic, multifactorial interventions to address these disparities in diabetes management are sorely needed.

Disparities in diabetes management have been linked to social determinants of health. Social and economic needs, including food insecurity, housing instability, and trouble paying for medical care, are common among racial/ethnic minorities and low-income populations.³ These needs interfere with adequate diabetes self-management behaviors, including healthy eating, physical activity, self-monitoring of blood glucose, and medication adherence,⁴⁻⁹ and are associated with high diabetes-related health care utilization.^{4,10-12} A recent meta-analysis indicated that diabetes self-management interventions are effective for reducing A1C by an average of 0.31% among racial/ethnic minorities,¹³ but access to these interventions is limited partly due to social determinants of health such as lack of transportation to attend sessions or access to the internet for online programs.^{14,15}

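### The refill outcome compared between arms is a count of delays that ignores their length, so a participant who stops refilling can score better than one who keeps refilling late

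*SAP*

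**What the plan says.** The last paragraph of the SAP defines the refill measure. "Delayed refills will be defined as medication not being dispensed for 7 days or more after the previous supply ran out". It then states: "For each participant, number of delays or gaps in refills and number of days without a refill will be calculated". So two refill quantities exist for each participant.

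Only one is carried into the analysis: "Both no-show visit rate and number of delays in refills are continuous variables". The distribution summaries follow for that pair, and then: "Assuming normal distribution, we will use the two-sample t-tests to compare the means of these two outcomes between the two study arms". The model is the same in scope: "We will use multiple linear regression modeling to examine the association between study arms and these two outcomes". Days without a refill has no planned summary, test or model.

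The SAP has no rule for a gap still open when follow-up ends, for participants with no diabetes medication to refill, or for combining several diabetes drugs.

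The protocol (Section 2, Phase 2, Aim 3, item e) names a different outcome at 6 months: "percent of on-time pharmacy refills for diabetes-related medications".

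**The concern.** An adherence score should get worse as a participant spends longer without medication. A count of delays need not do so. Each delay ends with a refill, and only after that refill can another delay begin. Someone who stops can have no further delays, so the count is capped at the point where adherence is worst.

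The trial compares navigation alone with navigation plus self-management training. One way the training could help is to bring participants who have lapsed back to refilling, even if late. On the delay count that improvement can register as harm. The adherence result is one of the preliminary effects meant to inform a full-scale trial, and a wrong sign would mislead that planning.

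**Working it through.** The documents give no numerical figure for the refill outcome, so there is nothing to reproduce. The check applies the SAP's definition to simple dispensing histories.

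**Inputs**
- From the SAP: a delay is 7 or more days undispensed after run-out, one per run-out.
- From the protocol: 6 months of follow-up, taken as 180 days; 50 participants per arm.
- Assumed, because the documents do not say: one drug, first fill on day 0, and supplies of 30, 60 or 90 days (S).

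**Participant A: every refill 8 days late.** Fills fall every S + 8 days. Days without supply = 8 × number of completed delays, as no further run-out falls inside the window.
- S = 30: fills on days 0, 38, 76, 114, 152; the last supply lasts to day 182. Delays 4; days 4 × 8 = 32.
- S = 60: fills on days 0, 68, 136; the last supply lasts to day 196. Delays 2; days 2 × 8 = 16.
- S = 90: fills on days 0, 98; the last supply lasts to day 188. Delays 1; days 8.

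**Participant B: stops after the first fill.** Delays 1, because the supply is undispensed for at least 7 days after run-out. Days = 180 − S.

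| Supply | Delays, A vs B | Days without supply, A vs B | Ratio of days, B/A |
|---|---|---|---|
| 30 days | 4 vs 1 | 32 vs 150 | 4.7 |
| 60 days | 2 vs 1 | 16 vs 120 | 7.5 |
| 90 days | 1 vs 1 | 8 vs 90 | 11.25 |

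The count ranks B better with 30- and 60-day fills and cannot separate the two with 90-day fills. Days without supply ranks B worse in every row.

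**Arm-level illustration (assumed mix).** Take 30-day fills and 50 per arm. In one arm 10 participants are like B; in the other 10 are like A; everyone else is on time.
- Mean delays: 10 × 1/50 = 0.2 versus 10 × 4/50 = 0.8. The sample variances are 0.2 × 0.8 × 1² × 50/49 = 0.163 and 0.2 × 0.8 × 4² × 50/49 = 2.612. SE = √((0.163 + 2.612)/50) = 0.236; t = 0.6/0.236 = 2.55; p = 0.012, in favour of the arm whose participants stopped.
- Mean days without supply: 10 × 150/50 = 30 versus 10 × 32/50 = 6.4, the opposite direction.

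This shows that the reversal can reach significance at the planned sample size. It does not show that the assumed mix will occur.

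**The protocol's measure.** With 30-day fills, and an unfilled supply counted as a refill due, A has 0 of 4 refills on time and B has 0 of 1. Both are 0%, so the reversal becomes a tie. Misranking can remain: a participant who refills on time on days 30 and 60 and then stops has 2 of 3 on time (67%) with 180 − 90 = 90 days without supply, and ranks above A at 0% with 32 days.

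**The case against.** Several points on the other side stand.

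- **Supply length.** The reversal depends on it. It is 4 versus 1 only with 30-day fills and disappears into a tie with 90-day fills. A tie still treats 8 and 90 days without supply as equal.
- **A score of 0 for stopping.** A reader might infer that a participant who never refills scores 0, because time to refill needs a dispensing date. The definition of a delay does not support this: a supply not dispensed for 7 days or more after run-out meets it without any later fill. The score is 1.
- **No fill during follow-up.** A reader might likewise infer that a participant with no fill in the period scores 0 and is among the least adherent. If an earlier supply ran out, the definition records a delay. If there was no earlier supply, there may be nothing to refill, since the Phase 2 inclusion criteria (Protocol, Section 5) do not require a diabetes prescription.
- **Frequency.** Long open gaps are plausible in this population but not documented. The poor follow-up described in the protocol concerns primary care visits, and it is absent from the Phase 2 inclusion list. No refill or discontinuation rate is given.
- **The protocol's measure.** Percent on time removes the reversal in the main example. It does not, however, rank the participant who stopped as worse, and the SAP does not plan to analyse it.
- **Importance.** This is one of five preliminary-effectiveness outcomes in a feasibility pilot. The feasibility aims and the A1C results are untouched. The better-ordered quantity is already calculated, so reporting it next to the count would expose a reversal.

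**Conclusion.** The point holds in limited form. Under the SAP's own definition, the only refill quantity compared between arms is capped at 1 per medication once a participant stops, while repeated late refilling can score higher. With one drug over 180 days, the late refiller scores 4 versus 1 or 2 versus 1 against the participant who stops, with 30- or 60-day fills, and the two tie with 90-day fills. The participant who stops has 4.7 to 11.25 times as many days without supply.

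It would go too far to say that the scale always runs backwards, or that the sign of the adherence result will be wrong. The supply lengths, the single drug and the arm-level mix are assumptions, and the documents give no stopping rate. What they support is that the planned comparison can give the wrong direction and that the SAP already derives a quantity without this fault. The importance lies between a minor suggestion and a recommended change.

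**What to change.** Amend the last paragraph of the SAP as follows.

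- Compare the number, or percent, of days without supply of diabetes medication between arms in place of the number of delays. Keep the number of delays as a descriptive summary.
- Count a gap still open at the end of follow-up up to that date, or up to a medication stop or disenrolment date where one is available. The change depends on this rule: if days were summed only over gaps closed by a later fill, the longest gaps would be lost.
- Limit the analysis to participants with a diabetes medication to refill.
- State how days are combined when a participant takes several diabetes drugs.
- Reconcile the SAP with the protocol's percent of on-time refills, for example by reporting it alongside, with an unfilled supply counted as a refill due.

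The cost is modest but is more than wording. The variable comes from pharmacy fill data, which the protocol (Section 5b) lists in the data warehouse. Prescription status and stop dates must also be read from the EHR; that section does not list them among the warehouse files. No new participant contact is needed.
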